Statistical Analysis	
• Phase I: The following decision rules will be followed: (i) If 0/3 dose limiting toxicities (DLTs) are observed proceed to enroll 3 more patients (ii) If 1/3 DLTs are observed enroll 3 more patients at the same treatment regimen. If 0/6 or 1/6 DLTs are observed, declare the regimen safe and as the maximum tolerated dose combination (MTD) of INCBO24360 in combination with the vaccine. If at least 2/3 or 2/6 DLTs are observed in Cohort 1, stop and de-escalate INCBO24360 to 100 mg BID in Cohort -1. If at least 2/3 or 2/6 DLTs are observed in Cohort -1, stop and de-escalate INCBO24360 to 50 mg BID in Cohort -2.• Phase IIb:• The Phase IIb component of this trial will consist of a randomized parallel design of n=25+25=50 patients =50 patients with treatment arms: (i) DEC205mAb-NY-ESO-1 fusion protein (CDX-1401) with adjuvant poly-ICLC alone and (ii) INCBO24360 in combination with the DEC205mAb-NY-ESO-1 fusion protein (CDX-1401) with adjuvant poly-ICLC. Stratification will be on clinical site (Roswell Park, U. of Pittsburgh). The primary endpoint will be progression free survival. Baseline is defined as the time following the treatment free interval, which can span 0 - 2 months, as described in Iasonos et al.[1] The primary analysis will be carried forth using a Cox proportional hazards model with factors corresponding to treatment and a continuous covariate adjustment for the length of the treatment free interval and a stratification factor for clinical site.• Phase I/IIb: The secondary analysis of continuous immunological response endpoints [antibody titers; NY-ESO-1 specific CD8⁺ and CD4⁺ frequency and function (IFN-γ ELISPOT and tumor recognition by CTL)] will be analyzed in a straightforward analysis-of-covariance (ANCOVA) fashion modeling post-treatment levels as a function of pre-treatment levels with factors corresponding to INCBO24360 (yes/no) and DEC205mAb-NY-ESO-1 fusion protein with adjuvant poly-ICLC (yes/no).• Exploratory Cohort: The analysis of continuous immunological response endpoints (e.g., antibody titers; NY-ESO-1 specific CD8⁺ and CD4⁺ frequency and function; frequency of memory T cell populations; TCR avidity) will be analyzed via an analysis-of-covariance (ANCOVA) fashion modeling post-treatment levels as a function of pre-treatment levels with factors corresponding to Sirolimus (yes/no) and DEC205mAb-NY-ESO-1 fusion protein with adjuvant poly-ICLC (yes/no).

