1.6.2.4 INCB024360 Clinical Studies

INCB24360-101 has been evaluated in Phase I study conducted by Incyte Corporation in subjects with refractory solid tumors. The study has used a 3+3 dose escalation design, with doses of INCB024360 ranging from 50 mg once daily (QD) to 700 mg twice daily (BID). Three subjects have initiated treatment at 50 mg QD, 4 subjects at 50 mg BID, 3 subjects at 100 mg BID, 6 subjects at 300 mg BID, 11 subjects at 400 mg BID, 5 subjects at 500 mg BID and 4 subjects at 700 mg BID.

INCB024360 has generally been well tolerated. The most common Grade 1 or Grade 2 AEs in $\geq 20\%$ reported have been fatigue, nausea, decreased appetite, vomiting, constipation, abdominal pain, diarrhea, dyspnea, back pain, and cough. The most common Grade 3 or Grade 4 AEs were

abdominal pain, hypokalemia, and fatigue (9.6% each). Despite 1 patient reporting a dose-limiting toxicity (DLT) of radiation pneumonitis at 300 mg BID, additional subjects were enrolled at this dose and no additional DLTs were reported. At 400 mg BID, 1 patient reported a DLT of Grade 3 fatigue, with no additional DLTs at this dose level. Another patient at 400 mg BID developed asymptomatic and transient hypopituitarism after 1 cycle of therapy and was able to continue dosing with INCB024360. Among the 18 subjects treated at either 600 mg or 700 mg BID, no DLTs were observed. Dose escalation was completed based on preliminary pharmacokinetic and pharmacodynamic data, which demonstrated that doses of INCB024360 above 300 mg BID achieved exposures exceeding the IC90 determined in nonclinical models and, in pharmacodynamic assays, reached a plateau for Kyn/Trp levels and ratios. In the final cohort of 600 mg BID, the effect of food on INCB024360 absorption was evaluated. No objective responses were reported. At 2 months, stable disease was seen in 15 patients and lasted \geq 4 months in 7 patients. The main AE reported in subjects receiving more than 2 cycles of INCB024360 has been Grade 1 or Grade 2 fatigue.

In a combination study conducted by Incyte Corporation of INCB024360 and ipilimumab in metastatic melanoma patients, 5 of 7 subjects enrolled at a dose of 300 mg BID of INCB024360 plus 3 mg/kg of ipilimumab, developed Grade 3 or Grade 4 AST and ALT elevations between 2 and 4 cycles of treatment. Only one of these subjects had a bilirubin elevation of Grade 1.

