The survival of patients with Stage III/IV ovarian cancer has been strongly correlated with the presence or absence of intratumoral T cells [34, 36]. Additionally, high levels of intratumoral IDO expression in ovarian cancer have been found to correlate with a reduced number of tumor infiltrating lymphocytes [37]. This high level of IDO expression was found to correlate with disease stage as well as with decreased survival, a finding that has been described by a number of investigators [38-41]. Thus, there is a strong rationale to utilize IDO inhibition as a strategy to restore antitumor immunity in advanced ovarian cancer.

Based on the safety profiles in Phase I and on-going Phase II studies, there is an extremely low potential for toxicity of the treatment combination. The vaccine (CDX-1401 with adjuvant polyICLC) has been shown to be safe in Phase I studies, with virtually no dose limiting toxicities, treatment-related Grade 3 or Grade 4 AEs, treatment-related SAEs or AEs requiring discontinuation of treatment. INC024360 has been tested in Phase I trials, and is currently undergoing Phase II evaluation. INC024360 was shown to be safe at doses as high as 600 mg bid. This is much lower than the maximum 300 mg bid that we propose in this clinical trial.

1.8 Rationale for Exploratory Cohort at Roswell Park ONLY (DEC205mAb-NY-ESO-1 Fusion Protein (CDX-1401) with Adjuvant Poly-ICLC in Combination with Sirolimus)

A major limitation of current cancer vaccines is the ineffective generation of memory T-cell precursors. This issue will be addressed in the current clinical trial via the use of sirolimus to promote the generation of effector/memory T-cells.

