3 METHODOLOGY

3.1 Study Design

This is an open-label, Phase I/IIb study of the IDO inhibitor, INCB024360, in combination with DEC205mAb-NY-ESO-1 fusion protein (CDX-1401) given with adjuvant poly-ICLC in patients with NY-ESO-1 or LAGE-1 expressing epithelial ovarian, fallopian tube, or primary peritoneal cancer who are in remission.

For the Phase I component of the study, eligible patients will receive a fixed intracutaneous dose of DEC205mAb-NY-ESO-1 fusion protein (CDX-1401) (Day 1) given with subcutaneous adjuvant poly-ICLC (Day 1 and Day 2) for each 28 day cycle for a total of 5 cycles; and Cohort 1 patient enrollment will begin INCB024360 at a fixed daily dose of 300 mg BID orally (Cohort 1) for a total of 7 cycles. Based on the decision rules for DLTs, patients may be enrolled into Cohort -1. Cohort -1 will receive DEC205mAb-NY-ESO-1 fusion protein (CDX-1401) (Day 1) given with adjuvant poly-ICLC (Day 1 and Day 2) for each 28 day cycle for a total of 5 cycles, and daily oral INCB024360 100 mg BID (Cohort -1) starting on Day 1 for 7 cycles. Based on the decision rules for DLTs, patients may be enrolled into Cohort -2. Cohort -2 will receive DEC205mAb-NY-ESO-1 fusion protein (CDX-1401) (Day 1) given with adjuvant poly-ICLC (Day 1 and Day 2) for each 28 day cycle for a total of 5 cycles, and daily oral INCB024360 50 mg BID (Cohort -1) starting on Day 1 for 7 cycles.

After completing 1 cycle of treatment in the last patient from Cohort 1 (or Cohort -1 or Cohort -2), accrual into the randomized Phase IIb study (Cohort 2) will begin at the dose of INCB024360 that is determined to be safe in the Phase I trial (300 mg BID versus 100 mg BID versus 50 mg BID) in combination with CDX-1401. This is a randomized parallel design employing randomization for each patient enrolled to 1 of 2 groups (**Table 1**). Treatment cohorts include (i) DEC205mAb-NY-ESO-1 fusion protein (CDX-1401) given with adjuvant poly-ICLC alone and (ii) INCB024360 plus DEC205mAb-NY-ESO-1 fusion protein (CDX-1401) given with adjuvant poly-ICLC.

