5.3 INCB024360

INCB024360 drug substance is a white to off white powder and is referred to herein as INCB024360. INCB024360 drug product will be provided as 25 mg, 100 mg, and 300 mg tablets. The tablet formulation contains the active ingredient along with commonly used excipients. The tablets contain the active drug (INCB024360) along with commonly used excipients Lactose Monohydrate, Microcrystalline Cellulose, Povidone, Croscarmellose Sodium Colloidal Silicon Dioxide, and Magnesium Stearate. All excipients are of compendial grade.

Source: Incyte Corporation [name]

Intended Dose: 50 mg, 100 mg, and 300 mg BID, depending on the cohort.

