6.3.1 Definition of Dose-Limiting Toxicity

Patients who do not complete the study through Day 29 for reasons other than dose limiting toxicities (DLTs) will be replaced. All patients will be included in the analysis results.

All AEs (as defined in **Section 9**) will be graded according to the NCI-CTCAE scale Version 4.0. Patients who experience a DLT will not receive any additional treatment (i.e., will be removed from the study and followed until resolution of their toxicity) and will not receive continued treatment even at a reduced dosage of the INCB024360 product. Patients with dose limiting toxicities requiring drug discontinuation (specified below) will be removed from the study (see exception for hypersensitivity reaction). The DLT period will be defined as 28 days after the first dose of vaccine. Late developing toxicities, occurring between Day 29 and Day 183 will be monitored throughout the study and according to the schedule of procedures and observations. Patients may be withdrawn from study even if DLT is due to INCB024360 or sirolimus alone. Safety monitoring will include careful assessment and appropriate reporting of AEs, as well as the construction and implementation of a data and safety-monitoring plan (Auditing, Monitoring, and Inspecting). Medical monitoring will include a regular assessment of the number and type of SAEs. Refer to the stopping rules for this study in **Section 6.3.2**. Any event(s) that might appear to trigger a treatment discontinuation rule or trial stopping rule will be discussed with the FDA review team. For phase IIb dose reductions for INCB024360 will be allowed (see section 6.3)

Management and dose modifications associated with AEs are outlined in **Section 6.3**. Refer to **Section 11** for statistical considerations and additional decision rules.

These events should be deemed to be possibly, probably or definitely related to study drugs. DLT criteria will be defined as any Grade 3 or higher treatment-related (i.e. definitely, probably, or possibly related) toxicity that occurs during the DLT evaluation period, including:

- Febrile neutropenia with standard of care treatment for ≥ 7 days. Growth factors may be used according to American Society of Clinical Oncology guidelines.
- Platelets $\leq 50 \times 10^9/L$
- Grade 3 or greater non-hematologic toxicity
- New onset pulmonary hypertension, interstitial pneumonitis or, CNS bleeding
- Serum bilirubin $> 3.0 \text{ mg/dL}$

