11 STATISTICAL METHODOLOGY

11.1 Primary Objective

For the Phase I component of the study 2 cohorts will be examined as described in the body of the project description. The following decision rules will be followed: (i) If 0/3 dose limiting toxicities (DLTs) are observed proceed to enroll 3 more patients (ii) If 1/3 DLTs are observed enroll 3 more patients at the same treatment regimen. If 0/6 or 1/6 DLTs are observed, declare the regimen safe and as the maximum tolerated dose combination (MTD) of INCB024360 in combination with the vaccine. If at least 2/3 or 2/6 DLTs are observed in Cohort 1, stop and de-escalate INCB024360 to 100 mg BID in Cohort -1. If at least 2/3 or 2/6 DLTs are observed in Cohort -1, stop and de-escalate INCB024360 to 50 mg BID in Cohort -2. It is anticipated that the probability of a DLT is rare in this setting. A Monte Carlo study using 10,000 replications was conducted. If the $\text{Prob(DLT)} = 0.2$ for Cohort 1 and $\text{Prob(DLT)} = 0.1$ for Cohort -1 or Cohort -2 then the expected sample size for the Phase I component of this study is 5.1 patients and the probability of declaring Cohort 1 as the MTD is 0.71 and the probability of declaring Cohort -1 or Cohort -2 as the MTD is 0.22. If the $\text{Prob(DLT)} = 0.1$ for Cohort 1 and $\text{Prob(DLT)} = 0.05$ for Cohort -1 or Cohort -2 then the expected sample size for the Phase I component of this study is 4.0 patients and the probability of declaring Cohort 1 as the MTD is 0.91 and the probability of declaring Cohort -1 or Cohort -2 as the MTD is 0.08. If the $\text{Prob(DLT)} = 0.5$ for Cohort 1 and $\text{Prob(DLT)} = 0.1$ for Cohort -1 or Cohort -2 then the expected sample size for the Phase I component of this study is 6.1 patients and the probability of declaring Cohort 1 as the MTD is 0.17 and the probability of declaring Cohort -1 or Cohort -2 as the MTD is 0.47.

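### When Cohort 1 passes, 0 or 1 DLT in 6 shows Cycle 1 tolerability of the highest dose tested; it does not determine an MTD or support an unqualified finding of safety

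*Combined protocol and SAP*

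**What the plan says.** **Rule.** Section 11.1 expands after no DLT in three ("i) If 0/3 dose limiting toxicities (DLTs) are observed proceed to enroll 3 more patients") and likewise after one in three. The passing condition is "If 0/6 or 1/6 DLTs are observed, declare the regimen safe and as the maximum tolerated dose combination (MTD". The failing branch is "If at least 2/3 or 2/6 DLTs are observed in Cohort 1, stop and de-escalate INCB024360 to 100 mg BID in Cohort -1", with a further step down to 50 mg BID. No branch goes up.

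**Doses.** Section 5.3 gives "Intended Dose: 50 mg, 100 mg, and 300 mg BID, depending on the cohort". Section 1.7 confirms the ceiling: "the maximum 300 mg bid that we propose in this clinical trial". Cohort 1 starts at that ceiling. The note to Table 1 records that 300 mg BID was chosen for Phase IIb after the Phase I safety review.

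**Window.** Section 6.3.1: "The DLT period will be defined as 28 days after the first dose of vaccine". INCB024360 is given for seven 28-day cycles. Under Section 3.1, Phase IIb opens "After completing 1 cycle of treatment in the last patient from Cohort 1" (or the lower cohort that passes).

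**Interval.** Section 11.3 plans a one-sided 95% Clopper-Pearson interval for the toxicity rate and specifies the lower limit.

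**Later toxicity.** Section 6.3.1 monitors late events from Day 29 to Day 183; Section 6.3.2 says Day 29 to Day 143. Section 1.6.2.4 reports an earlier study of INCB024360 300 mg BID with ipilimumab in metastatic melanoma, where 5 of 7 subjects "developed Grade 3 or Grade 4 AST and ALT elevations between 2 and 4 cycles of treatment".

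**The concern.** The rule attaches two conclusions to one count, and the count supports neither as worded.

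An MTD is a statement about the dose above it: that dose was tried and was not tolerated. A design that starts at its top dose and can only step down gives no such information when the first cohort passes.

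*Safe*, without qualification, describes a seven-cycle regimen, but the count behind it covers Cycle 1 in six patients. Safety of the combination is the Phase I primary objective. As written, the trial could report an MTD that it did not determine, and a safety conclusion broader than its data, as the basis for assigning 25 Phase IIb patients to seven cycles of INCB024360.

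**Working it through.** **1. The plan's own figures.** Section 11.1 gives the probability of declaring Cohort 1 the MTD as 0.71, 0.91 and 0.17 at DLT probabilities 0.2, 0.1 and 0.5. Under the written rule the cohort always reaches six unless at least 2 of the first 3 have a DLT. Two DLTs in three already means at least two in six, so

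P(declare) = P(X ≤ 1 | n = 6, p) = (1−p)^6 + 6p(1−p)^5.

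| p | Stated | Written rule | Rule that accepts at 0/3: (1−p)^3 + 3p(1−p)^5 |
|---|---|---|---|
| 0.2 | 0.71 | 0.655 | 0.709 |
| 0.1 | 0.91 | 0.886 | 0.906 |
| 0.5 | 0.17 | 0.109 | 0.172 |

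The stated figures fit a rule that stops and accepts at 0/3, not the rule as written. That is a separate discrepancy. I use the written rule below; the other rule would be more lenient.

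**2. What the rule says about an MTD.** At p = 0.02: 0.98^6 + 6(0.02)(0.98^5) = 0.886 + 0.108 = 0.99. A dose with almost no toxicity is labelled the MTD nearly every time, because nothing above it is tried. Section 1.6.2.4 reports no DLTs in 18 single-agent subjects at 600 or 700 mg BID. That is not evidence on the combination, but it gives no reason to think 300 mg BID is a ceiling of tolerance.

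**3. What 0/6 or 1/6 says about the 28-day DLT rate.**

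- 0/6, upper: 1 − 0.05^(1/6) = 0.393. Lower: 0.
- 1/6, upper: solve (1−p)^6 + 6p(1−p)^5 = 0.05, p = 0.582. Lower: 1 − 0.95^(1/6) = 0.0085.
- Pass probability at p = 0.30: 0.7^6 + 6(0.3)(0.7^5) = 0.118 + 0.303 = 0.42. At 0.40 it is 0.23.

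The limit named in Section 11.3 would therefore be 0% or 0.9%. A lower limit shows how small the rate cannot be; a safety statement needs to know how large it might be.

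**4. Coverage of the window.** 7 × 28 = 196 planned days of INCB024360, and 28/196 = 14%. Both late-toxicity periods (Day 183 and Day 143) end before Day 196.

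**5. Effect of onset after Day 28.** Take a total rate of 30% for some severe toxicity, and let a share s occur inside the window. The documents do not give s, so it is an assumption. P(declare) at p = 0.30s:

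| s | 0 | 0.25 | 0.50 | 1 |
|---|---|---|---|---|
| P(declare) | 1.00 | 0.93 | 0.78 | 0.42 |

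**6. Timing of the ipilimumab signal.** The cycle length in that study is not given. With 28-day cycles, Cycle 2 starts on Day 29, outside the window. With 21-day cycles it starts on Day 22, partly inside. If the phrase means after two completed cycles, onset is from Day 42 (21-day) or Day 56 (28-day), outside on either assumption.

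**The case against.** The strongest reply has four parts.

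*Later toxicity is acted on.* Section 6.3.2 pauses the study for any Grade 4 event and suspends accrual for a related death or related Grade 4 event, with no 28-day limit. Section 6.3 has Phase IIb dose-modification criteria for related Grade 3 or higher toxicity outside the DLT period, naming AST/ALT. Section 11.5 has safety evaluated weekly and lets the committee stop the trial, and Section 10 adds committee review of both phases. All of this stands, so a reader who infers that events after Day 28 count for nothing would be wrong. What remains is narrower: none of these provisions feeds the 0/6 or 1/6 declaration. Six related Grade 3 events in Cycle 3, for example, would trigger neither the pause nor the suspension rule, although the committee could still act.

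*The liver signal belongs to another combination.* This also stands. It arose with ipilimumab in melanoma, and Section 1.6.1.2 reports no DLTs and no treatment-related Grade 3 or 4 events in 21 patients given CDX-1401 with an adjuvant. A reader might infer that this regimen is known to cause late hepatic toxicity. The documents do not show that. The signal is a warning that the protocol itself cites.

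*MTD is only loose terminology.* In part. If a higher cohort fails and a lower one passes, the label is defensible. Section 1.6.2.4 also gives a pharmacodynamic reason for not going above 300 mg BID: exposure beyond the IC90 and a plateau in the kynurenine and tryptophan measures. That justifies choosing the dose; it does not make it an MTD.

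*The intervals are those of any six-patient cohort.* True. They do not show a peculiar flaw in the rule. They show that the word attached to its result is too strong.

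**Conclusion.** The point holds in a limited form. When Cohort 1 passes, the trial has shown that the highest dose tested was tolerated in Cycle 1 by at least five of six patients. It has not determined an MTD. Its 28-day DLT rate could be as high as 39% (0/6) or 58% (1/6), and a true 30% rate would pass 42% of the time. The lower limit in Section 11.3 cannot support a safety conclusion. The case in question is the one that went forward, since Table 1 records 300 mg BID as the Phase IIb dose; the documents do not give the DLT count that led there.

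The figures assume the written rule, independent patients, a common DLT probability and six evaluable patients. The illustration of late onset depends on an assumed share inside the window.

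A reader might go further and conclude that 300 mg BID is unsafe, or the wrong dose for Phase IIb. Nothing here supports that. The finding concerns what the Phase I result may be said to show.

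**What to change.** 1. In the synopsis and Section 11.1, replace the declaration of safety and MTD with a statement that Cohort 1 was tolerated in Cycle 1 and is carried forward as the Phase IIb dose, and that no MTD is determined when Cohort 1 passes.
2. Report the 28-day DLT rate with its exact one-sided 95% upper limit, and correct the lower-limit statement in Section 11.3.
3. Beside the DLT result in the Phase I safety conclusion, tabulate related Grade 3 or higher events in the Phase I patients from Day 29 to 30 days after the last INCB024360 dose. The synopsis already has adverse events collected to that point, and Table 7 has all grades reported in Phase I.
4. Reconcile the 28-day window in Section 6.3.1, the Day 183 and Day 143 periods in Sections 6.3.1 and 6.3.2, and the onset reported in Section 1.6.2.4. Which period or clinical rule is right is for the investigators to settle.

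The cost is wording in three places, one table from existing data and a reconciliation of the timing passages; no extra patients are needed. The stated Phase I conclusion becomes less favourable.
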